1.1. Pre-measurement

In this study, 19 athletes aged 16-30 years with a history of unilateral lower extremity injury and 20 athletes who have not had a lower extremity injury before were included. The MMSE (Mini Mental State Examination) score of each athlete was calculated. Before starting the measurements, the "Informed Consent Form" was signed by the participants. Before starting the performance measurements, the Mini Mental State Test was applied to the participants. For the cognitive task, the backward digit test of the Wechsler intelligence scale (WISC) was preferred. For the randomized number sequence to be used during dual task measurements to be of suitable difficulty for the cognitive level of the person, a 2-digit random number sequence was first told once, as one digit per second, and the person was asked to say the same number sequence in reverse. For each correct answer, the number of digits of the said number sequence is increased by one. The number of digits in which the person made a mistake was recorded and one more digit of this number was used during the measurements.

1.2. Balance Measurement

Biodex Balance System SD device was used for balance measurement. The device, which has a circular floor, four regions to represent 5° tilt in each region, and four quadrants to measure instability in anterior-posterior-medial-lateral directions, consists of 12 difficulty levels according to tilt formation resistance. The device, which can be used for both analysis and rehabilitation purposes, has different measurements and exercise modes. In calculating the instability level, mathematical formulas are used that consider the time spent by the person in the relevant regions and quadrants in each repetition. Athlete Single Leg Stability was preferred among the test modes included in the Biodex Balance System SD balance device. After the person's name, age and height information were entered into the database of the device, the screen of the device was adjusted to be at eye level according to the height of the athlete. The tests were applied to both legs in a randomized order twice, both as a single task and a dual task with cognitive task. The person took a position with his/her eyes open, the foot of the untested leg resting on the back of the ankle of the tested leg, his/her arms crossed on his/her chest, and the center of balance in the middle of the platform most comfortably. In this position, the coordination of the point where the heel touches the ground and the angle of the foot are recorded in the system. The content of the test was explained to athletes. The analysis protocol was applied at 5 difficulty levels, consisting of 20 seconds, 1 sample and 3 test repetitions, with a 10 second rest between repetitions. In the dual task measurement, while the athlete is in the resting position on the platform, standing behind the athlete is the randomized number in the previously determined number of digits. The sequence was sung twice, approximately one digit per second, in a speaking voice. As soon as the second repetition was finished, the athlete took the test position, and the measurement was carried out. At the end of the measurement, the athlete was asked to say the said number sequence in reverse and the number sequence he said was recorded. A new number sequence is given after every 20 seconds of measurement. During the tests, the related test was canceled and repeated in cases such as opening the arms because of loss of balance, contacting the ground in the air, changing the coordinate of the foot on the ground. General stability index (OSI), anterior/posterior stability index (APSI), medial/lateral stability index (MLSI) were recorded.

1.3. Functional Hop Test Measurement

All the jump tests were applied to each leg separately. The test was repeated in cases where athlete touched the ground with his/her other foot, could not maintain his/her stability during the descent, and received support with his/her hand. For each jump, 1 sample and 2 measurements were applied on each leg. Hops were measured twice as a single task and a

dual task with cognitive task. During the dual task, while the athlete was in the ready position at the starting line, the random number sequence with the previously determined digits was repeated 2 times, standing behind the athlete, with a speaking voice, approximately one digit per second. After the second repetition, the athlete was asked to start jumping. At the end of the jump, the athlete was asked to say the said number sequence in reverse and the number sequence he/she said was recorded.

## **COVER PAGE**

## TITLE: Analysis of Balance and Functional Hop Tests in Athletes with Lower Extremity Injuries by Dual Task Study

## NCT05484778

**Document Date: 03.06.2021** 

## 1. Statistical Plan

Statistical analysis was made with IBM SPSS 22 package program. Shapiro Wilk test was used to evaluate the fit for normal distribution. It was found that the data showed normal distribution. Repeated measures ANOVA analysis was used for group comparisons of the variables. Before-after comparisons without group separation

Paired sample T-test was used for the level of statistical significance was taken as p 0.05. In the statistical analysis, the before after comparison applied to all participants without group discrimination was used to support interpretation of the significance of the comparisons made between groups.

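### The non-randomised group comparison states no adjustment for recorded age and height, no leg term and no injured-leg contrast, although both legs were tested under both tasks.

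*SAP*

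**What the plan says.** Protocol section 1.1 describes 19 athletes "with a history of unilateral lower extremity injury and 20 athletes who have not had a lower extremity injury before". The groups are defined by injury history, and the stated age range is 16 to 30 years.

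Both legs were measured. In section 1.2 the balance tests were "applied to both legs in a randomized order twice, both as a single task and a dual task with cognitive task". In section 1.3, "All the jump tests were applied to each leg separately", again as single and dual task. Each injured athlete therefore has an injured-leg and an uninjured-leg value for each task.

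Age and height exist as data: section 1.2 says that "age and height information were entered into the database of the device".

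SAP section 1 gives the between-group analysis in one complete sentence: "Repeated measures ANOVA analysis was used for group comparisons of the variables". It lists no within-athlete factor, leg term, choice of control leg, injured-leg contrast or covariate, and no other section supplies them. The sentence after it, on the paired t-test without group separation, is visibly broken in the text, so the SAP's silence should be read with some caution.

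**The concern.** There are two separate issues.

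**Adjustment.** The groups were not randomised. An unadjusted group main effect mixes any injury effect with whatever difference in age or height happens to exist between 19 and 20 athletes. Both variables were recorded, so adjustment needs no new data.

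**Legs.** The injury is on one side. Several analyses fit the SAP sentence: leg coded injured/uninjured, leg coded left/right, legs averaged, or legs entered as separate observations. They estimate different things and have different error properties. A reader cannot tell which leg a reported group difference refers to. Depending on the choice, a deficit confined to the injured leg could be diluted, or the type I error could exceed the nominal 5%.

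**Working it through.** The documents give no sample size calculation, effect size, SD or between-leg correlation, so there is no planned figure to reproduce. The inputs are 19 and 20 athletes (Protocol 1.1) and a significance level of 0.05 (SAP 1), taken as two-sided. Effect sizes, between-leg correlation ρ, covariate strength and imbalance are assumptions. Power is from the noncentral t distribution.

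**1. Injured leg v one control leg.** SE = √(1/19 + 1/20) = 0.3204 SD, df = 19 + 20 − 2 = 37. For a 0.8 SD deficit, power is 68%.

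**2. Legs averaged.** SE = 0.3204 × √((1+ρ)/2). If the other leg carries a share s of the deficit, the averaged effect is 0.8 × (1+s)/2, that is 0.4 SD for s = 0, 0.6 SD for s = 0.5 and 0.8 SD for s = 1.

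| ρ | SE | Power, s = 0 | Power, s = 0.5 | Power, s = 1 |
|---|---|---|---|---|
| 0.3 | 0.258 | 33% | 62% | 85% |
| 0.5 | 0.277 | 29% | 56% | 80% |
| 0.7 | 0.295 | 26% | 51% | 75% |
| 0.8 | 0.304 | 25% | 49% | 73% |

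Averaging equals the single-leg contrast when (1+s)/2 = √((1+ρ)/2), so s = 2√((1+ρ)/2) − 1. This is 0.61 at ρ = 0.3 and 0.90 at ρ = 0.8. Below that share averaging loses power; above it, averaging gains. With left/right coding, the group main effect is also a mean over the two legs, so the same dilution applies to it.

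**3. Legs treated as independent (38 v 40).** The naive SE is too small by a factor √(1+ρ). Type I error = 2 × (1 − Φ(1.96/√(1+ρ))) = 8.6%, 11.0% and 13.3% at ρ = 0.3, 0.5 and 0.7. A simulation of 40,000 runs per value gave 8.4%, 11.0% and 13.5%.

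**4. Confounding of the group main effect.** Bias in SD units = (covariate-outcome correlation r) × (group imbalance in SD). The rejection rate under no injury effect follows from step 1 with the bias as the effect.

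- r = 0.3, imbalance 0.3 SD: bias 0.09, type I error 5.9%.
- r = 0.3, imbalance 0.5 SD: bias 0.15, type I error 7.4%.
- r = 0.6, imbalance 0.5 SD: bias 0.30, type I error 15%.

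This does not carry over directly to group-by-task. A covariate effect that adds equally to single and dual task cancels in the difference between tasks. Section 1.1 also sets the digit load from each athlete's own result ("one more digit of this number was used during the measurements"), which limits one further route.

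**5. Price of adjustment.** Two covariates leave df = 35, with SE = 0.3204 × √((1−R²) × VIF). For two groups of nearly equal size, VIF ≈ 1 + imbalance²/4, so a 0.8 SD imbalance gives 1 + 0.64/4 = 1.16.

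- R² = 0, VIF = 1.16: power for 0.8 SD falls from 68% to 62%.
- R² = 0.1, 0.2, 0.3, VIF = 1: power becomes 73%, 77% and 83%.

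**The case against.** The strongest reply is that this is thin reporting, not a wrong analysis. A reader might infer that the legs were in fact averaged and the injured-leg effect missed. The documents do not say so. If leg was coded injured/uninjured, neither the dilution nor the inflated type I error arises. This stands, and the leg point is conditional.

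Nor is averaging always the poorer choice. If both legs are equally affected, it has 73-85% power against 68%. The documents do not say how far the other leg is affected, so this stands too.

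A reader might also infer that injured leg v control leg should lead. That does not follow. If the deficit really is confined to one leg, then at 0.8 SD the group-by-leg contrast has 54%, 68%, 88% and 97% power at ρ = 0.3, 0.5, 0.7 and 0.8, against 68% for the between-group contrast on that leg. The study title also points to the dual task, which a contrast averaged over tasks would hide. The choice of lead is a trade-off.

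On covariates, an unadjusted ANOVA can be legitimate, the moderate cases move type I error only to 5.9-7.4%, and adjustment can cost power. A reader might infer that the groups differ in age or height, but no imbalance is shown. What remains is that a non-randomised comparison leaves out two recorded variables without saying why, when including them costs little.

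**Conclusion.** The concern holds in conditional form. What the documents establish is a non-randomised comparison with no stated covariate, leg term or injured-leg contrast, in a design that yields the data for all three. The covariate point applies whatever leg coding was used, but chiefly to the group main effect, and its size depends on an imbalance that the documents neither show nor exclude. The leg point depends on an unstated coding: a fall from 68% to 25-33% power if legs were averaged and a 0.8 SD deficit sits in one leg only, no loss or a gain if the other leg is nearly as affected, and about 9-13% type I error if legs were taken as independent at ρ of 0.3 to 0.7. If leg was already coded injured/uninjured, only the covariate point remains. The documents do not support saying that the analysis was wrong. This is a cheap improvement.

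**What to change.** - Fit group x leg x task with leg as a within-athlete factor coded injured/uninjured. Assign control athletes' legs to these two slots in the same left/right proportion as in the injured group.
- Adjust for mean-centred age and height.
- Report, with 95% CIs, the group effect for the injured leg, the group-by-leg contrast and group-by-task. The investigators should choose and name the lead contrast, and the single v dual task comparison should stay visible.
- Label these analyses post hoc if results are known. The SAP is in the past tense and already reports a finding from the data ("It was found that the data showed normal distribution").

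**Cost.** No new measurements are needed if injury side is on record; the word unilateral implies it, but Protocol sections 1.1 to 1.3 do not list it. Adjustment uses about 2 of 37 degrees of freedom. In the worst case shown, power for 0.8 SD goes from 68% to 62%; where age and height explain 10-30% of the variance without imbalance, it rises to 73-83%. Confounding by factors the documents do not list as recorded, such as sport or training level, would remain.

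### The before-after t-test pooled over injured and uninjured athletes has no group contrast, so it cannot support the interpretation of between-group significance

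*SAP*

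**What the plan says.** All the analysis text is in SAP section 1, Statistical Plan. It gives two tests:

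- For groups: "Repeated measures ANOVA analysis was used for group comparisons of the variables".
- For the whole sample: "Before-after comparisons without group separation", for which the adjoining line names the paired t-test.

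It then links them, saying that the "before after comparison applied to all participants without group discrimination was used to support interpretation of the significance of the comparisons made between groups". It does not say how that support works, and it does not name the group-by-task interaction.

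The groups are defined in Protocol 1.1. The injured group is "19 athletes aged 16-30 years with a history of unilateral lower extremity injury"; the comparison group is made up of 20 with no earlier injury of that kind. The documents describe no separate before and after time points. The only within-athlete pair in the Protocol is the task condition: in 1.2 the balance tests are done "both as a single task and a dual task with cognitive task", and 1.3 does the same for the hops. I therefore read before-after as single against dual task. That is an inference.

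**The concern.** The study compares injured with uninjured athletes, and the pooled test ignores which athletes were injured. Its result says whether performance changes on average. The SAP uses it for a different purpose, as support when interpreting whether the groups differ.

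Two wrong conclusions become easier. A chance group difference may be trusted more because athletes in general do worse under the dual task. A real group difference may be doubted because the average change is small or because the two groups' changes cancel.

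**Working it through.** The plan states no power, SD or effect size, so there is no planned figure to reproduce.

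**Inputs.** From the Protocol: n = 19 injured and 20 uninjured. From the SAP: significance level 0.05. Assumed: two-sided testing, normal changes, one change d (dual minus single) per athlete, and effects expressed in SDs of d.

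**Step 1: what each test estimates.**

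- Pooled paired t-test: (19·μ_inj + 20·μ_uninj)/39 = 0.
- Group-by-task interaction: μ_inj − μ_uninj = 0. With two conditions and no leg factor, this is the two-sample t-test on d.
- Group main effect: concerns each athlete's average over the two tasks, which cancels out of d.

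The pooled test therefore contains neither group contrast.

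**Step 2: are the two estimates linked by chance?** With change SDs s₁ (injured) and s₂ (uninjured), the covariance of the pooled mean change and the group difference in change is

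(19/39)(s₁²/19) − (20/39)(s₂²/20) = (s₁² − s₂²)/39.

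With equal SDs this is zero, so one estimate carries no information about the other.

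**Step 3: rejection rates with equal SDs.** An equal change δ in both groups gives the pooled test a noncentrality of δ√39; for δ = 0.5 this is 0.5 × 6.245 = 3.12, power 86%. An injured-only change Δ gives the interaction Δ/√(1/19 + 1/20); for Δ = 0.8 this is 0.8/0.3204 = 2.50, power 68%. An injured-only change Δ has the same average as Δ × 19/39 in everyone, for example 0.8 × 19/39 = 0.390. The rates below come from the exact noncentral t or from simulation.

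| Scenario (SD of change) | True group difference in change | Pooled significant | Interaction significant |
|---|---|---|---|
| 0.5 in both groups | none | 86% | 5% |
| Injured only, 0.5 | 0.5 | 30% | 33% |
| Same average, 0.244 in both | none | 32% | 5% |
| Injured only, 0.8 | 0.8 | 60% | 68% |
| Same average, 0.390 in both | none | 66% | 5% |
| Injured only, 1.0 | 1.0 | 78% | 86% |
| Same average, 0.487 in both | none | 84% | 5% |
| +0.5 injured, −0.475 uninjured | 0.975 | 3% | 84% |

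At a matched average change, the pooled test is significant about as often without a group difference as with one. In the last row the average is (19 × 0.5 − 20 × 0.475)/39 = 0, so a large group difference would find no support. A pure difference in level of 1.0 SD of the change (within-athlete correlation 0.5 assumed) leaves the pooled test at 5%, while the group main effect is significant in 94%.

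**Step 4: sensitivity to unequal SDs, no effect of any kind.** The two estimates now share sampling error.

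| Change SD, injured v uninjured | Correlation of estimates | Interaction significant (false positive) | Pooled significant when interaction is | Pooled significant when interaction is not |
|---|---|---|---|---|
| 1 v 1 | 0 | 5.0% | 4.8% | 5.0% |
| 1.25 v 1 | 0.22 | 5.1% | 7.1% | 4.9% |
| 1.5 v 1 | 0.385 | 5.4% | 11.7% | 4.6% |
| 1 v 1.5 | −0.385 | 4.8% | 12.1% | 4.6% |
| 2 v 1 | 0.60 | 5.6% | 21.6% | 3.9% |
| 1 v 2 | −0.60 | 4.9% | 23.5% | 4.0% |

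A chance interaction is then more likely to be accompanied by a significant pooled test. With a real injured-only change of 0.8 (units of the smaller SD), pooled significance with v without a significant interaction is 53% v 32% at 1.5 v 1, but 30% v 54% at 1 v 1.5. The apparent support reverses with which group varies more.

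**Step 5: precision of the direct comparison.** With equal SDs, the 95% CI half-width for the difference in change is t(0.975, 37) × √(1/19 + 1/20) = 2.026 × 0.3204 = 0.65 change SD. Welch half-widths, in units of the smaller SD, are 0.83 to 0.84 at a ratio of 1.5:1 and 1.03 to 1.05 at 2:1.

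**The case against.** The strongest reply is that the SAP claims only support for interpretation. The group comparison has its own test, the pooled result is not a gate, and no p-value or error rate changes. Reading an overall task effect beside a group comparison is ordinary practice, because it shows whether the cognitive task altered performance at all. The section is also loosely worded, so reading one sentence closely may be ungenerous.

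Much of this stands. The interaction keeps its error rate, the pooled test is legitimate for the overall task effect, and nothing in the documents shows that a wrong conclusion was drawn. The unequal-SD figures are sensitivity results without any basis in the documents. They are also conditional on a false positive: both tests are falsely significant together in only about 11.7% × 5.4% = 0.6% of analyses at 1.5 v 1, and 21.6% × 5.6% = 1.2% at 2 v 1. One change per athlete is simpler than a design with two legs and several outcomes, so the rates illustrate the problem and do not describe the trial's own analyses.

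It does not rescue the sentence. That sentence is intact, and what it names as supported is the interpretation of between-group significance, which a test without a group term cannot inform. The equal-SD comparison is enough to show this. The argument does not depend on what before-after means, since any paired test pooled over the groups lacks the contrast.

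**Conclusion.** The concern holds. The SAP gives the pooled paired t-test an inferential role that it cannot fill. The absence of a group contrast is a matter of algebra and needs no assumption. The zero link between the two estimates needs equal change variances and independent athletes. The percentages rest on assumed effects, normal changes and one change per athlete.

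This should be fixed, but it does not invalidate the ANOVA. What is at risk is the credibility given to group findings.

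**What to change.** In SAP section 1, delete the sentence that uses the pooled comparison to interpret between-group significance. Replace it with one stating that:

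- the pooled paired t-test is reported only as the overall task effect;
- any conclusion that dual-task cost differs by injury rests on the group-by-task interaction of the repeated measures ANOVA, reported as the difference in cost with a 95% CI;
- a group main effect is reported separately, as an overall difference in level.

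The section already reports a finding from the data ("It was found that the data showed normal distribution"), so a re-run is probably post hoc. If results have been seen, it should be labelled so.

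The cost is one sentence out and one in, with the same data and software. There is also a cost in candour: with intervals as wide as those in Step 5, a non-significant interaction must not be read as equal dual-task cost in the two groups.
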